4. STUDY DESIGN

4.1 Description of Study Design

We will be recruiting a total of 136 participants, between the ages of 18-60. Participants will be enrolled in this study based on the presence of active eosinophilic esophagitis and adherence to the inclusion and exclusion criteria.

[figure not shown]
We intend to conduct a prospective non-blinded randomized trial that compares a 1-food elimination diet (1FED) versus a 6-food elimination diet (6FED) for six weeks (Phase 1). Subsequently, non-responders to 1FED dietary elimination therapy will be treated with 6FED and non-responders to 6FED will be treated with SGC (swallowed fluticasone at a dose of 880 mcg twice a day) for six weeks (Phase 2) while on an unrestricted diet, if the participant chooses to continue in to Phase 2. The empiric dietary therapy interventions are as follows: 1-food elimination diet (1FED)—avoidance of milk vs. 6-food elimination diet (6FED)—avoidance of milk, egg, wheat, soy, fish/shellfish, and peanut/tree nuts, for six weeks. Milk elimination for both 1FED and 6FED includes all mammal milk (i.e. goat, sheep, and cow's milk must all be eliminated). The study design is shown schematically in Figure 1 Study Design Flowchart.

In Phase 1, all participants will be randomized 1:1 to either 1 food elimination (milk elimination alone, 1FED) or 6 food elimination (milk, egg, wheat, soy, fish/shellfish, peanut/tree nuts elimination, 6FED) therapeutic diet. At the end of this phase, an EGD will be performed to assess remission. Attainment of remission (esophageal eosinophil counts <15 eosinophils/high powered field) after Phase 1 will result in study discontinuation and maintenance of the “successful” dietary therapy. Treatment non-responders may choose whether or not to continue into Phase 2. Dietary therapy non-responders who were on 6FED in Phase 1 and continue in to Phase 2 will receive topical swallowed steroids for six weeks (Phase 2) followed by EGD with esophageal biopsies. These participants will return to an unrestricted diet (i.e. stop 6FED) prior to beginning topical swallowed steroid therapy. Dietary non-responders in Phase 1 who were on 1FED and continue in to Phase 2 will continue to a 6FED therapeutic diet (Phase 2) for six weeks followed by EGD with esophageal biopsies to assess remission.

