5.3 Exclusion Criteria

Individuals who meet any of these criteria are not eligible for enrollment as study participants:

1. Inability or unwillingness of a participant to give written informed consent or comply with study protocol
2. Have been treated with topical swallowed steroids within the last 2 months or systemic steroids within the last 3 months
3. Have pathological eosinophilia in segments of the GI tract other than the esophagus determined by local review
4. Have been diagnosed with a GI malabsorption disorder (i.e., Inflammatory bowel disease, Crohn's disease) or Celiac disease
5. Are currently on dietary therapy avoiding milk or on a 6FED.
6. Have concurrent *H. pylori* gastritis or parasitic infection

7. Have history of anaphylaxis to milk (with current avoidance of milk)
8. Unable to complete study procedures, including EGD.
9. Have previously failed strict dietary therapy clearly documented with one of these regimens or topical steroid treatment (i.e. have not achieved histological remission of <15 eos/hpf after having been on 2 mg of budesonide per day or 1760 mcg of fluticasone per day for 8 weeks prior to the EGD).
10. Use of investigational drugs within one month prior to enrollment
11. Are concurrently receiving any of the prohibited medications listed in section 8.3
12. Not fluent in English
13. On immunotherapy for pollen (if not on maintenance therapy) or IgE-mediated food allergy.
14. Past or current medical problems or findings from physical examination or laboratory testing that are not listed above, which, in the opinion of the investigator, may pose additional risks from participation in the study, may interfere with the participant's ability to comply with study requirements or that may impact the quality or interpretation of the data obtained from the study.

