9.2 Enrollment (Week 0)

All eligible participants will be enrolled into the study at Week 0 if they meet all entry criteria and have completed the screening procedures. Study procedures will not be repeated if the enrollment visit takes place within 5-10 business days of the screening visit. At this visit, staff members will:

- Assess eligibility (inclusion and exclusion criteria)
- Measure vitals (blood pressure, heart rate, respiratory rate, temperature), height and weight
- Obtain stool sample (if possible and not collected at Screening/Baseline) from subjects who have consented to stool collection
- Administer patient reported outcome questionnaires, which will include dietary questionnaires to measure *intake* of the food allergens and a food diary to assess baseline diet
- Completion of DSQ
- Assess concomitant medications and/or therapies

- Skin testing for allergies including prick and patch testing
- Randomize eligible participants to the 1FED or 6FED diet
- Provide standardized dietary instructions for 1FED or 6FED
- Research lab samples
 - Blood serum (~1-2 tsp, or 5-10 mL) for food IgE, CRD, and IgG4
 - Blood serum (~3-6 tsp, or 15-30 mL) for T cell studies

The participants will be encouraged to call the PI and/or study coordinator if they have any questions, concerns, adverse events, or changes in medication.

Stool samples may be collected from participants who have consented to stool collection at the Enrollment visit if they were unable to be obtained at the Screening/Baseline visit. Stool will only be collected at some, but not all, participating centers.

9.3 Phone Visits, Phase 1

A study staff member will conduct three phone visits (at weeks 1, 3, and 5) during Phase 1 in order to monitor participants' progress throughout the trial. The following procedures will occur during these phone visits:

- Assess con-med and/or con-therapy compliance
- Assess AEs
- Determine compliance with treatment
 - A dietary questionnaire to measure *intake* of the food allergens will be completed by the participants during weeks 1 and 5
 - A food diary will be completed by participants during weeks 1 and 5 to measure adherence
- Daily completion of the DSQ within the two weeks prior to the Phase 1 EOT EGD (Weeks 4 and 5)

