11.1 Participant Completion

Participant completion is defined by completion of the EGD at the end of Phase 1 and Phase 2 (for those who choose to continue into Phase 2); there are two levels of completion, those that complete Phase 1 and those that complete Phase 2.

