The instructions for the 1FED and 6FED therapeutic diets will be standardized across sites by providing consensus documents produced by registered dietitians who are experts in dietary elimination in EoE. There are currently no validated dietary questionnaires for measuring food allergen intake in adults in the US. Dietary intake and *consumption* of the allergens will be measured at the start of the trial and adherence to the dietary elimination (i.e. *avoidance* of the allergens) during the trial will be measured using modified versions of the NCI's usual dietary intake/diet history questionnaires and 3-day food diaries (<http://cancercontrol.cancer.gov>). Stool samples may be collected from subjects who consent to stool collection to evaluate the effect of diet on the microbiome.

Similarly, standardized instructions for using SGC will be provided, based on our prior studies. We have chosen to use fluticasone propionate (FP) rather than budesonide in this study, given our prior work in this area, and our recent finding that high-dose fluticasone is well tolerated and highly effective, and our preliminary findings concerning esophageal transcripts that predict responsiveness to FP therapy. The study design is shown schematically in Figure 1 Study Design Flowchart.

Figure 1 Study Design Flowchart

Analysis Populations

The analysis population for the primary and secondary endpoints will be the intent-to-treat population with the goal of including patients who have been randomized in the analyses. However, we will exclude patients who were inappropriately randomized and never completed the enrollment visit. Patients for which the primary endpoint of histological remission cannot be determined will be imputed as treatment failures. To maximize comparability with other studies, we will also perform per protocol analyses, including only individuals who complete the study phase of interest for all proposed studies.

Variables of Interest

Primary outcome:

- 1) Remission rate (<15 peak eosinophils/hpf)

Secondary outcomes:

- 1) Change in eosinophils/hpf from baseline to post treatment
- 2) Remission status: Patients will be classified into 3 remission categories: complete histological remission (≤ 1 peak eosinophils/hpf); partial remission (2-14 peak eosinophils/hpf); no remission (≥ 15 peak eosinophils/hpf)

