- 3) Histology Scoring System (HSS): Will include the overall score, grade score, stage score, and the inflammatory and structural sub-scores. Scores will be reported as distal, proximal, and maximum
- 4) HSS score by remission status (complete, partial, and no remission).
- 5) Endoscopy Scoring System (EREFS): Will include the overall score and the inflammatory and fibrostenotic sub-scores. Scores will be reported as distal, proximal, and maximal score.
- 6) EoE Diagnostic Panel (EDP): The summary EoE score (EDP total score) will be a secondary outcome.

Derived Variables.

- 1) HSS scores. Sum of the feature scores divided by the maximum possible score for the biopsy for grade and stage. The total score is the sum of the grade and stage scores. Inflammatory sub-scores include the following features: eosinophils, abscesses, surface layering, and surface necrosis. Structural sub-scores include basal layer hyperplasia, dilated intercellular spaces, apoptotic epithelia, and lamina propria fibrosis.
- 2) HSS remission. HSS remission is defined as a having both a grade and stage total score less than or equal to 3 and an eosinophil grade score no greater than 1. This is calculated separately for distal and proximal biopsies. When both distal and proximal biopsies are in remission, this is considered complete remission, when only one of the two biopsies meet these criteria, it is partial remission. When neither meet these criteria, it is no remission. Analyses will include full remission vs other and full+partial remission vs no remission.
- 3) EREFS. Total EREFS score will be calculated by summing the grades for all five of the features. The inflammatory score contained the sum of the exudate, edema, and furrows scores (this could range from 0 to 5), and the fibrostenotic score contained the sum of the rings and stricture scores (this could range from 0 to 4).
- 4) Adherence. Adherence will be dichotomized into mostly adherent vs not-mostly adherent. The judgement of adherence will be based on questionnaires about food intake and dietitian input. If inconsistent, food diaries will be reviewed. The final adherence call will be provided to the statistician.
- 5) Atopy. Atopy is a multi-faceted disease. Individuals will be defined as atopic if they report a history of asthma, eczema, allergic rhinitis, allergic conjunctivitis, IgE mediating food allergy

and/or atopic dermatitis.

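### The SAP's per-protocol set is a completer set with no adherence condition, so no planned analysis is restricted to patients who followed their assigned diet

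*SAP*

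**What the plan says.** The SAP (Analysis Populations) bases the primary and secondary endpoints on the intent-to-treat population and counts patients with undetermined remission as failures. It then adds that "we will also perform per protocol analyses, including only individuals who complete the study phase of interest". It does not say what completing a phase means. Protocol 11.1 does: "Participant completion is defined by completion of the EGD at the end of Phase 1 and Phase 2". Neither place mentions following the diet.

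Adherence is dealt with elsewhere. The SAP (Study design) says that what will be measured is "adherence to the dietary elimination (i.e. *avoidance* of the allergens) during the trial", and Protocol 4.1 has the same description. Item 4 of the SAP's Derived Variables states: "Adherence will be dichotomized into mostly adherent vs not-mostly adherent". The call rests on intake questionnaires and dietitian input, with food diaries consulted if these conflict. No cut-off for mostly is given. The SAP lists adherence among the covariates to be considered in the primary model and in the models for secondary objectives 2 to 5. Protocol 4.4 (sub-aim 2a) relates compliance to response, and Protocol 13.4.5 describes accidental exposure to the eliminated foods.

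Protocol 13.4.3 separately plans a complete-case analysis, set beside the failure-imputed and multiply imputed results.

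**The concern.** A per-protocol analysis is normally read as showing the effect in patients who took the treatment as assigned. Here the treatment is a diet, the trial is open-label, and adherence is acknowledged to be difficult (Protocol 3.2). A set defined by completion alone differs from the intent-to-treat set in how it treats patients who did not complete, and in little else. If the two results agree, that says something about missing outcomes and nothing about diet adherence. A reader who sees the per-protocol label may nevertheless take the agreement as evidence that non-adherence did not matter.

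The question is whether removing five further food groups adds remission. Patients on 6FED who kept eating a restricted food, and patients on 1FED who dropped more than milk, would both tend to narrow the difference. The planned set would expose neither. Because adherence is described as avoidance, nothing requires the second kind of deviation to be recorded at all.

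**Working it through.** **1. Who is in each set.**
- A 6FED patient who kept eating wheat and had the week 6 endoscopy is in the intent-to-treat set, the complete-case set and the SAP's per-protocol set. Protocol 11.2 permits termination of a patient who cannot comply with the diet but does not require it.
- A patient with no endoscopy is in the intent-to-treat set as a failure and in neither of the others.
- A patient who withdraws early but has the biopsies that Protocol 9.4 schedules at that visit has an outcome, so could enter the complete-case set. Whether that patient completed the phase is unclear. The two sets are therefore close, but the documents do not make them identical.

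**2. Where adherence enters.** It enters as a candidate covariate (inclusion optional, measured after randomisation), in the exploratory link between compliance and response, and in the description of accidental exposure. None of these restricts an analysis to patients who followed their diet.

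**3. The plan's own figure.** Protocol 13.6 assumes remission of 45% on 1FED and 70% on 6FED, two-sided alpha 0.05, and 60 per group for at least 80% power. With the pooled normal formula, n = [1.960 × √(2 × 0.575 × 0.425) + 0.842 × √(0.45 × 0.55 + 0.70 × 0.30)]² / 0.25² = (1.370 + 0.569)² / 0.0625 ≈ 60.2, so 61 per arm. Power at 60 per arm is 79.9% by this formula and 80.6% by exact enumeration of the likelihood ratio test that the plan names. The figure reproduces.

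**4. Illustration of dilution in a completer set.** Let a be the share of 6FED completers who deviate and remit at 45%, and b the share of 1FED completers who over-restrict and remit at 70%. Then the 6FED rate is 70 − 25a, the 1FED rate is 45 + 25b, and the difference is 25 × (1 − a − b) points. Power is for 60 per arm.

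| a = b | 6FED | 1FED | Difference | Power |
|---|---|---|---|---|
| 0 | 70% | 45% | 25 points | 80% |
| 10% | 67.5% | 47.5% | 20 points | 60% |
| 20% | 65% | 50% | 15 points | 38% |
| 30% | 62.5% | 52.5% | 10 points | 20% |

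The shares are assumptions, and so is full conversion to the other arm's rate.

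**5. What an adherence condition would recover.** On the same assumptions, a call based on avoidance removes a but not b. At 10% the difference becomes 70 − 47.5 = 22.5 points, and at 20% it becomes 70 − 50 = 20 points. The remainder can be judged only if intake of the other foods on 1FED is reported.

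**6. What it costs in numbers.** Excluding 10, 20 or 30% of 60 leaves 54, 48 or 42 per arm. If the difference in that set were 25 points, power would be 76%, 70% or 64%.

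**The case against.** The strongest reply is that the trial already compares the diets. Intent-to-treat is primary, it compares the diets as assigned, and its result does not depend on how any per-protocol set is defined. All of that stands. A reader might infer that the two diets are never compared, or that non-adherence is ignored; the documents do not support either. Adherence is a candidate covariate, and compliance is related to response. What remains is narrower: the covariate is optional and measured after randomisation, and no analysis is restricted by adherence.

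A reader might also infer that entry criteria bias the 1FED arm, because Protocol 5.3 excludes only patients who "Are currently on dietary therapy avoiding milk or on a 6FED", so someone already avoiding wheat or egg can enrol. This does not follow. Baseline diet precedes randomisation, so such patients are expected equally in both arms, and all must have had active disease on biopsy to enter. It describes the population; it is not an arm-specific bias.

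A third temptation is to exclude 1FED patients who dropped extra foods. That would select on post-randomisation behaviour in one arm only, and could introduce a bias of its own. The documents do not say that the 1FED arm's questionnaires cover all six food groups, and they state that no validated US adult instrument exists. On the other hand, nothing in writing stops the dietitian from noting over-restriction.

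Finally, the plan tests superiority of 6FED and plans no non-inferiority claim. The risk that a small difference is read as near-equivalence therefore concerns interpretation and is not a planned inference.

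**Conclusion.** The point holds in a limited form. The SAP's per-protocol set has no adherence condition, keeps completers who did not follow the assigned diet, and is close to the protocol's complete-case analysis under a label that implies more. The SAP already derives an adherence call that could define the set and does not use it for that purpose.

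This rests on reading completion in the SAP through Protocol 11.1, since the SAP does not define it. The size is unknown because the documents give no rate of non-adherence or over-restriction. The fall from 25 to 20 points with 10% deviating in each arm is an upper-end illustration: it gives every deviator the other arm's full remission rate, even for a single food. It should not be read as an estimate of what will happen. The primary analysis is not called into question.

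**What to change.** - Rename the present set completers and state that completion means the end-of-phase endoscopy, saying how early withdrawals with a biopsy are classed.
- Define the per-protocol set as completers judged mostly adherent under item 4 of Derived Variables. Write down beforehand what mostly means, and have the call made without knowledge of histology.
- Report by arm the intake of the eliminated food groups, including the non-milk groups on 1FED, as far as the week 1 and 5 questionnaires or food diaries (Protocol 9.3) capture it. Use this as description, not as a reason for exclusion. Confirm first that the 1FED forms cover those foods.
- Optionally, add a supportive analysis in patients eating all six food groups at baseline. This is fixed before randomisation, so it avoids post-randomisation selection.

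The cost is SAP wording, a blinded adherence call and one descriptive table. The adherence call rests on food intake, so a per-protocol set for the Phase 2 fluticasone group would need its own stated criterion. The drawback is that the adherence-based set is smaller and no longer protected by randomisation. It should be labelled supportive, with intent-to-treat kept as primary.

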3. STUDY HYPOTHESES/OBJECTIVES

3.1 Hypotheses

We hypothesize that 6FED will be superior to 1FED, although we expect that a substantial (meaningful) percentage of patients will respond to 1FED.

We hypothesize that some patients who fail to respond to 1FED will respond to 6FED.

We hypothesize that some patients who fail to respond to 6FED will respond to SGC.

We hypothesize that HSS will more accurately quantify histological changes associated with EoE and be reversible following each therapeutic intervention. Furthermore, we hypothesize that some patients may show partial responses, where a subset of the HSS may be improved earlier or in dissociation with eosinophil levels, for example.

We hypothesize that molecular biomarkers will change (improve) with each treatment phase, at least in part. Furthermore, we hypothesize that biomarkers may reveal (a) novel insight into therapeutic resistance and/or relapse; (b) reveal patient sub-groups not identified by histology; and (c) ultimately prove to be readily usable biomarkers in clinical settings and possess personalized medicine value. If our hypotheses are proven to be correct, they have potential to transform monitoring of patients during therapeutic intervention, by identifying molecular markers that have therapeutic significance, and also by reducing the need for biopsies, particularly after therapy is initiated.

We hypothesize that the therapeutic interventions utilized in this study will improve clinical symptoms as measured by PRO metrics.

We hypothesize that certain patient phenotypes will correlate with response to each intervention in the trial.

We hypothesize that skin test results (prick testing to the 6 test foods and atopy patch testing to milk) will provide significant predictive value for outcomes in the diet trial phases.

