- 2) To evaluate the effect of each therapy on histological remission defined by a variety of changes in eosinophils, including (a) pre- minus post-therapy peak eosinophil counts; (b) partial

remission (2-14 peak eosinophils/hpf); and (c) complete histological remission (≤ 1 peak eosinophils/hpf).

- 3) To evaluate the effect of each therapy by utilizing the histology scoring system (HSS) created to express the severity and extent of other abnormalities in the gastrointestinal (GI) tract that often accompany eosinophilic inflammation.
- 4) To evaluate endoscopic outcomes as assessed by the endoscopy scoring system (EREFS).
- 5) To determine the impact of each therapeutic intervention on biomarkers using the EoE Diagnostic Panel (EDP).

For secondary objectives 1, the remission rate at the 6-week time point for non-responders in Phase 1 who proceeded to Phase 2 will be summarized separately depending on the treatment patients received during Phase 1. The 95% two-sided confidence interval for the rate will be provided. If the remission rate is missing for patients that entered Phase 2, it will be imputed as a treatment failure.

To test hypotheses for each of the secondary objectives 2-5, treatment group comparisons at the end of Phase 1 will be performed using the generalized linear mixed effects model using the link that is appropriate for the endpoint (i.e. logit for binary, cumulative logit for ordered multinomial categories, identity for continuous). These models will account for the clustering within sites and will consider sex, baseline esophageal eosinophil count, adherence, presence of atopy, and time since diagnosis as covariates. For continuous data, appropriate transformations will be considered (e.g. log, square root, rank) to satisfy the assumptions of the analyses. If the remission status for the categorical outcomes is missing, we will evaluate how to treat the observation. If the study subject prematurely quit the clinical trial, then we will consider the observation a treatment failure. However, if the data was not captured (as in the case of a biopsy which did not capture both distal and proximal findings then we will consider imputation. Missing data for continuous outcomes may be imputed using multiple imputation techniques. Covariates for imputation will include investigative site, sex, presence of atopy and duration of disease. Secondary outcomes 2-5 will be tested at the two-sided $\alpha=0.01$ to account for multiple testing.

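### The SAP's HSS remission cut-off of 3 cannot fail on the HSS scale the SAP defines (at most 1 for grade, 1 for stage, 2 in total), so the rule does not test the non-eosinophil features

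*SAP*

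**What the plan says.** Both definitions are in the SAP, Derived Variables.

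- **Item 1 (HSS scores).** The grade and stage scores are each the "Sum of the feature scores divided by the maximum possible score for the biopsy for grade and stage". Then: "The total score is the sum of the grade and stage scores". The item names four inflammatory features (eosinophils, abscesses, surface layering, surface necrosis) and four structural ones: "Structural sub-scores include basal layer hyperplasia, dilated intercellular spaces, apoptotic epithelia, and lamina propria fibrosis". It gives no numeric range for any feature.
- **Item 2 (HSS remission).** "HSS remission is defined as a having both a grade and stage total score less than or equal to 3", with the further requirement of "an eosinophil grade score no greater than 1". The rule is applied to the distal and the proximal biopsy separately. Both in remission counts as complete, one as partial, neither as none. Two dichotomies follow: "Analyses will include full remission vs other and full+partial remission vs no remission".

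Secondary objective 3 in the SAP describes the HSS as "created to express the severity and extent of other abnormalities in the gastrointestinal (GI) tract that often accompany eosinophilic inflammation". Protocol 4.3 and 6.4.2 list HSS features but give neither a scale nor a remission rule. The ratio in item 1 is therefore the only HSS scale in either document.

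**The concern.** The threshold and the scale, set out in consecutive items, do not match. A programmer who follows both literally gets a grade-and-stage condition that every biopsy meets. The variable would then classify biopsies without regard to hyperplasia, intercellular spaces, apoptosis, fibrosis or the extent of any feature. Those are the abnormalities that objective 3 uses the HSS to describe.

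At stake are the two HSS remission contrasts between the diets. A difference, or the absence of one, could be reported as a finding on overall histology when the rule had not required the other abnormalities to resolve. A programmer who notices the mismatch would have to choose a unit that the SAP does not state. In a trial where the sponsor and investigators know the assigned diet (protocol 4.6), that choice should be on record before the data are analysed.

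**Working it through.** **Inputs.** Score = feature sum / maximum possible sum (SAP item 1). Total = grade + stage (item 1). Cut-off 3 on grade and stage, and 1 on the eosinophil grade (item 2). Eight named features (item 1). The documents give no feature range, so a range is assumed only where marked.

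**Step 1: range check (no assumption needed).**
- Grade ≤ maximum/maximum = 1, and likewise stage ≤ 1.
- Total ≤ 1 + 1 = 2.
- If the 3 applies to each score, 1 < 3. If it applies to the sum, 2 < 3. The condition always holds.
- Distance: 3/1 = 3 times the single-score maximum; 3/2 = 1.5 times the total maximum.

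Enumerating every possible sum for 7 or 8 scored features, with assumed feature maxima from 1 to 5, gives no ratio above 3 in any scenario.

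**Step 2: what is left of the rule.** Only the eosinophil condition remains, and item 2 does not state its unit.
- *Raw feature score:* it can fail if the feature maximum exceeds 1. HSS remission then depends on the eosinophil grade alone, and the other 8 − 1 = 7 features and all stage scores drop out.
- *Also a ratio:* a ratio cannot exceed 1, so this condition cannot fail either. Every evaluable biopsy is in remission.

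On both readings the non-eosinophil features and the stage scores are inert.

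**Step 3: illustration (assumed: 8 features, each scored 0 to k for grade and for stage; eosinophil condition raw).** Set the eosinophil grade to 1 and everything else to its maximum k. Grade ratio = (7k + 1)/(8k); stage ratio = 8k/8k = 1.

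| k | Grade ratio | Stage ratio | Total | Undivided grade, stage |
|---|---|---|---|---|
| 2 | 15/16 = 0.94 | 1.00 | 1.94 | 15, 16 |
| 3 | 22/24 = 0.92 | 1.00 | 1.92 | 22, 24 |
| 4 | 29/32 = 0.91 | 1.00 | 1.91 | 29, 32 |

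Each biopsy is in HSS remission as written. On undivided sums each would fail a cut-off of 3, taken per score or summed. This is a deliberately extreme case that shows what the rule permits. It is not an estimate of how often it would occur.

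**Step 4: would undivided sums settle it?** The cut-off would then bind. With 8 features and assumed maxima of 1, 2, 3 and 4, the possible sums above 3 number 5 of 9, 13 of 17, 21 of 25 and 29 of 33. One ambiguity remains: undivided grade 3 and stage 3 pass if judged separately (3 ≤ 3 twice) but fail if summed (3 + 3 = 6 > 3).

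**Step 5: can the 3 be converted to a ratio?** An undivided 3 equals 3/(features × maximum). With 8 features and maxima of 1 to 4 this is 0.375, 0.188, 0.125 and 0.094. If only 7 features were scored (assumed), it is 0.429, 0.214, 0.143 and 0.107. Item 1 sets the denominator per biopsy, so there is no single equivalent.

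**The case against.** The best reply is that the 3 was plainly meant for undivided sums. The eosinophil condition makes most sense as a raw score, it stands in the same sentence, and a consistent raw reading leaves no empty condition. The HSS is also a separately cited instrument whose scale may be set out in its source. The likely intent can be granted. But the SAP does not state it, and item 1 uses the term total score for the sum of two ratios. The item that follows does give numeric ranges for the EREFS sub-scores, so the omission here is not house style. Even with raw sums accepted, the separate-or-summed question in Step 4 stays open.

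Three stronger conclusions are tempting, and the documents do not support them.

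- *That HSS remission simply becomes another eosinophil measure.* This holds only if the eosinophil condition is raw while the 3 is on the ratio scale. On a consistent ratio reading, the variable does not discriminate between evaluable biopsies at all.
- *That the cut-off costs the trial its hypothesis that* "a subset of the HSS may be improved earlier or in dissociation with eosinophil levels" *(protocol 3.1).* Even a repaired HSS remission requires a low eosinophil grade, so it could not show improvement elsewhere while that grade stays above 1. This limit comes from how the variable is built. The hypothesis is served by the overall, grade and stage scores and the inflammatory and structural sub-scores, which the SAP lists as secondary outcomes and which this error does not touch.
- *That many participants would be misclassified.* Nothing in the documents allows a count.

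**Conclusion.** The inconsistency is certain: it follows from dividing a sum by its maximum and needs no outside figure. As written, the cut-off of 3 excludes no biopsy, and non-eosinophil features and stage scores cannot influence HSS remission. Whether anything then discriminates depends on the unstated unit of the eosinophil condition.

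The reach is limited to one derived variable and its two contrasts, which would not require the other abnormalities in objective 3 to resolve. HSS remission is not itself a numbered secondary outcome. The primary endpoint, remission by eosinophil count, and the continuous HSS scores and sub-scores stand as planned. The SAP should be corrected because, followed literally, it gives a wrong classification; the point does not threaten the trial's main conclusion.

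**What to change.** Before programming, amend Derived Variables item 2 to state:

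1. that the cut-off of 3 applies to the undivided sum of feature scores, if the sponsor confirms that this was meant;
2. whether it applies to grade and stage separately or to their sum;
3. that the eosinophil condition is on the raw feature score.

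If the sponsor instead intends the ratio scale, it must specify and justify a new cut-off, below 1 if applied to each score. That would be a new threshold rather than a wording repair, because the per-biopsy denominator rules out a simple conversion of 3.

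The first route costs about two sentences in the SAP. It needs no new data and leaves the other analyses unchanged.
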